NCT04060212

Microbial mechanisms of methylmercury metabolism in humans.

[name].

**Department of Environmental Medicine
[name]**

1. Background and Purpose of study.

1 A. Application Background. This submission seeks approval of a new study that follows essentially the same protocol of two prior approved studies we have conducted, with a modification that includes an additional intervention of administration of a prebiotic to influence change in the gut microbiota. The prior studies were #RSRB00050613 entitled Methylmercury metabolism and elimination in humans and #RSRB00057934 entitled Determination of methylmercury metabolism and elimination status in humans.

1 B. Purpose of the study.

The overall objective of this study is to investigate the role of gut microbes in mediating how humans metabolize and excrete the environmental neurotoxicant methylmercury (MeHg). Our secondary objectives are: 1) to derive non-invasive tools to evaluate an individual's MeHg metabolizing potential, 2) to identify dietary supplement approaches to enhance an individual's capacity to metabolize and excrete toxic MeHg, 3) to discover symbiotic bacterial strains with probiotic potential. Successful completion of the study Aims will eventually lead to advanced methodologies to better assess the risks of Me Hg on human health and identify factors that mitigate this risk.

1 C. Scientific Background.

MeHg impact on human health. Exposure to MeHg through consumption of fish continues to pose a health risk for many populations globally. The developing nervous system is a preferred target for MeHg toxicity, making the fetus and young children most vulnerable. Conflicting results from large epidemiological studies has lead to uncertainty in advising the public on mercury risks associated with fish consumption [1-3]. At odds are the potential harmful effects of Me Hg and the beneficial effects of dietary nutrients and antioxidants in fish. A great deal of uncertainty for this conflict stems from the fact that MeHg metabolism and elimination rate is known to vary widely from individual to individual. This translates into the possibility that two individuals consuming the same amount of fish with the same frequency could, unknowingly, experience as much as 4-fold difference in MeHg in their bodies. Thus, there is a need for greater understanding of the mechanisms of MeHg metabolism and elimination, as well as for development of tools to assess these characteristics in people.

MeHg toxicokinetics: the importance of elimination rate. Orally ingested MeHg is absorbed very efficiently in the intestine with 95% of the dose typically being taken up and distributed to the bloodstream [4]. MeHg undergoes rapid transport and equilibration between blood and target organs [4]. Subsequent to an initial "spike" in concentration, mercury levels in blood resolve to a slow steady rate of decline that is dictated by the overall elimination rate of Me Hg from the body [4-6]. Elimination rates,

expressed as half time ($t_{1/2}$), range from <30 to >120 days, demonstrating the existence of “fast” and “slow” MeHg metabolizers [4-11]. The elimination rate of MeHg is a major determinant for accumulation of MeHg to the elevated steady state levels that occur in people who consume fish on a regular (e.g. weekly or daily) basis. The ability to determine the MeHg metabolism and elimination status of an individual is therefore a means of prospectively identifying “fast” versus “slow” metabolizers.

Mechanisms of MeHg metabolism and elimination: the critical role of de-methylation. Approximately 90% of the MeHg ingested and absorbed in the body is ultimately excreted via the feces [5, 7]. The current dogma holds that MeHg excretion occurs via the liver, where glutathione-MeHg conjugates are transported via bile to the small intestine [12]. However, a “vicious cycle” exists in that MeHg can be rapidly re-absorbed in the intestine and returned to circulation [13]. This cycle can be broken by MeHg de-methylation, which yields Hg^{++} , a poorly absorbed inorganic (iHg) form of mercury [14]. This mechanism is consistent with observations that Hg stemming from a MeHg dose is typically found as 90-100% iHg in the feces [15]. Rodent studies, using variations in diet and antibiotics, reinforce two principles regarding MeHg de-methylation: 1) it is a rate-limiting step in elimination of MeHg and, 2) it is supported by the microbiota of the gut [16] [17]. The mechanism by which human gut bacteria might de-methylate MeHg remains unclear. Furthermore, distinct species of bacteria with MeHg degrading activity within the human gut have yet to be characterized. Nonetheless, MeHg degrading bacteria in the environment, common to sediments and soils, have been well characterized. Such MeHg degrading strains carry a mercury (Mer) locus, which harbors genes encoding alkylmercury lyase (MerB) and mercury reductase (MerA) that encode enzymes capable of de-methylating MeHg and reducing Hg, respectively [18]. There is a possibility that related strains of microbes carry these genes in the human gut.

A new method to measure MeHg metabolism in people. We have recently overcome a significant barrier to implementing kinetic studies of MeHg in people by developing a simple, non-invasive protocol for sampling MeHg metabolism and excretion over time. We have published this in two papers, both stemming from prior IRB-approved human studies. In short, we accomplish this by assaying two samples of biological media: human hair and feces. Through application of current technology and instrumentation (i.e., laser ablation-ICP-mass spectrometry (LA-ICP-MS)) we have established a protocol to quantify MeHg elimination rate ($t_{1/2}$) and correlate it with demethylation (fecal iHg:MeHg ratio) in individuals who have previously eaten just three fish meals. We are now in a position to capitalize on this methodology to extend our investigations of the microbiota of the human gut to identify the mechanisms and the bacterial species responsible for MeHg metabolism and excretion.

1D. Specific Aims.

It should be noted that the human subject portion of this proposed study is part of consortium among the P.I. ([name], U of R) and co-investigators at Montana State University (MSU), Drs. [name] and [name]. This study will be supported by NIH VICTER mechanism specifically designed to support such “Virtual Consortium” with three investigators. **As such, all aspects of human subject recruitment and bio-sample collection and sample coding will be performed in Aim 1.** Aims 2 and 3 will

involve studies in mice and with defined bacterial cultures and will be conducted with de-identified samples of feces or fecal DNA at Montana State University.

Our scientific premise is that symbiotic microbes in the human gut are required for the efficient biotransformation and excretion of toxic MeHg. There is substantial evidence, including our own, that the rate of MeHg elimination in the human body relies on gut microbiota. Importantly, we discovered that MeHg elimination kinetics in an individual can vary significantly over time and, furthermore, is significantly slowed when taking antibiotics [10, 11]. Our initial findings with microbiome characterization yielded logical candidate bacterial taxa that now require validation to test their role in MeHg elimination [19]. With this evidence, we **hypothesize that a susceptibility for reaching harmful levels of MeHg in the body is dictated by select members of the human gut microbiome that: a) carry out MeHg demethylation to enhance excretion, b) are variably present or variably abundant between and within individuals over time and c) are metabolically responsive to diet supplementation.** Our Specific Aims are:

Aim 1. Establish gut microbiome samples that exhibit “fast” and “slow” MeHg kinetics in humans.

Aim 2. Validate the microbiome’s role in MeHg kinetics using germ-free/gnotobiotic mouse modeling.

Aim 3. Identify and isolate microbial species responsible for MeHg demethylation in the human gut.

2. STUDY DESIGN

2A. Overview

Study site: This study will involve human subjects recruited from the greater Rochester area and will be conducted in the URMC Department of Environmental Medicine. Hg analyses and DNA extraction of fecal samples will be performed in the U of R Environmental Health Science Center (EHSC) Elemental Analysis Facility. Fecal samples will also be evaluated for MeHg demethylation activity by assaying bacterial enzyme activity in Rochester. Hg analyses of hair samples by LA-ICP-MS will be done at the Trace Element Analysis lab at Dartmouth College, New Hampshire. Additional studies, exempt from IRB approval, will be done at Montana State University with de-identified samples of human feces and fecal DNA that are shipped to co-investigators [name] and [name] at MSU.

Protocol: Subjects will follow a protocol of eating three fish meals within a two-week period to incur exposure to naturally occurring levels of MeHg in the fish. Fish meals will consist of 6-12 ounces of commercially available tuna steaks. This will be followed by an elimination period of 60 days where no fish or seafood is to be consumed. Single hairs collected at 60 days after the last of the three fish meals will be used to determine a MeHg elimination rate using LA-ICP-MS to perform longitudinal Hg elemental analysis as we have previously reported [10]. De-methylation of MeHg coming from the fish will be determined by direct analysis of iHg and MeHg in fecal samples collected

approximately four weeks following the final fish meal. Fecal samples will also be used for culture assays and for direct iHg/MeHg analysis to determine of MeHg demethylation rates *in vitro* and *in vivo*, respectively (Biotransformation, $B_{in\ vitro}$ and $B_{in\ vivo}$). Fecal DNA will be used for metagenomic analyses to profile type and abundance of all bacterial species present. Statistical correlations between elimination rate, demethylation rate and abundance of bacteria will be used to deduce strains of bacteria that contribute to demethylation and overall metabolism and elimination of MeHg. The above protocol will be performed in two separate “trials” (which are denoted as “Study Periods” to the

[figure not shown]

Figure 1. Protocol Overview.
Elimination rate determination, k_{el} ;
Demethylation (Biotransformation)
analysis, $B_{in\ vitro}$ and $B_{in\ vivo}$.

participants in the consent form) within the course of approximately 10 months and separated by an intermediate “washout” period of 4 months (Figure 1). Subject will not be required to refrain from fish or seafood during this washout period. Prior to the second trial subjects will receive a commercially available over the counter prebiotic (Prebiotin™) to be orally self-administered on a regular schedule for the entire trial 2 period. This prebiotic is not the subject of this investigation in this study, and is simply selected for its known effects of shifting gut microbial composition to enrich for healthier strains of bacteria (e.g. Bifidobacteria). Fecal sampling prior to and subsequent to prebiotic will be used to document changes in the microbiota for each individual. The prediction is that prebiotic induced change in the gut microbiota will result in a change in MeHg metabolism kinetics in each

individual.

2B. Rationale for Study Design

The main rationale for this study design is based on our evidence that de-methylation of MeHg in the human gut is the driving force for faster elimination MeHg that comes with eating fish. We therefore predict that with the methods we now have available to measure MeHg kinetics, coupled that with high-resolution analyses of gut microbiome characteristics in individual people who have undergone a controlled exposure to MeHg, we can resolve a microbial basis for MeHg metabolism in humans. This is an ambitious undertaking, and hence, is designed as a consortium project to be executed by three investigators with respective expertise in 1) human MeHg kinetics, 2) mouse microbiome manipulations and 3) microbial metagenomics and culturing methods. By design, the human subject component of the study is to be carried out at URMC. The objective is to capture “slow” and “fast” MeHg metabolizing human microbiome samples, that can be handed off to colleagues at MSU for specialized analyses that do not involve the human subjects, simply their de-identified samples.

3. CHARACTERISTICS OF THE RESEARCH POPULATION

(Many of the characteristics below are reiterated from our previously approved project: RSRB00050613 entitled *Methylmercury metabolism and elimination in humans* and RSRB00057934 entitled *Determination of methylmercury metabolism and elimination*

status in humans.)

3A. Subject Characteristics

Number of Subjects: We aim to obtain data on 40 adults, 20 males and 20 females, for this study. We will therefore target consent of 46 participants (23 women, 23 men) to account for potential drop out. We expect the recruitment will be achieved locally in the Rochester area including the URMC community, but will not exclude interested people from outside this region. With the limited exclusion criteria below, we anticipate completing recruitment within the first several months of the study.

Gender and Age of Subjects: Study subjects will aim to be comprised of an equal number of men and women with no restriction on age ranging from 18 to 80.

Racial and Ethnic Origin: There will be no restrictions on racial or ethnic origin in subject recruitment. It is anticipated the racial and ethnic diversity of the study group will reflect the various ethnicities that comprise the general population of the greater Rochester metropolitan area.

Dental amalgams: Dental amalgams are a source of inorganic mercury. This study is not directed at inorganic mercury and prevailing literature indicates that inorganic mercury stemming from amalgams will not affect the biological and metabolic processes of MeHg under investigation here. Nonetheless, we will identify presence or absence of amalgams in subjects so that we can account for the contribution of this inorganic source of Hg to the Hg content measured in feces. This will be critical for evaluating the extent of MeHg demethylation that has occurred in each subject.

Vulnerable Subjects: Vulnerable subjects potentially include students and staff of the University of Rochester. Advertisements will be placed in areas where they may be seen by students, employees and the general public. For students and staff of the University of Rochester consent forms will clearly delineate that refusal to participate will have no consequence on job status, work place relationships, grades, or any other benefits to which the student/staff will otherwise be entitled.

3B. Inclusion and Exclusion Criteria

Inclusion Criteria:

- Subjects must be 18-80 years in age.
- Subjects must be in good general health based on self-reported health status, with the exception of self-reported conditions listed in the exclusion criteria.
- Subject must be willing to comply with study procedures.

Exclusion Criteria:

- Known allergy to fish.
- Pregnant or lactating women.
- Use of hair dyes or chemical treatments within the prior month and/or intent to use such treatments during the two trial periods. (Hair treatment during the washout period up to one month prior to the second trial is acceptable).
- Known gastrointestinal or renal disorders.
- Subjects with diminished mental capacity.
- Use of antibiotics within two months leading up to the study.

3C. Discussion of Subject Population

The inclusion criteria are very broad and it is anticipated a large diversity in age and ethnicity will result. This is acceptable as age and ethnicity, although not primary study objectives in this pilot, are likely to produce variation in MeHg metabolism and elimination status, the determination of which is an objective of the study. Exclusion criteria are defined based on factors that are likely to result in either harm to the subject or to substantially alter the metabolic processes or analytical procedures of MeHg and thus obscure results. Of particular concern is exposure to the fetus or infant to MeHg, which is known to target the developing nervous system. This concern warrants exclusion of pregnant or breast-feeding women.

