4. SUBJECT IDENTIFICATION, RECRUITMENT, CONSENT AND COMMUNICATION

4A. Method of Subject Identification and Recruitment

Subjects will be recruited through local advertising by posting RSRB-approved flyers around the University of Rochester Medical Center. Response via phone and email to these postings will be anticipated. The P.I. and Lab personnel will also inform friends and acquaintances about the study. Lab personnel will be prepared to tell interested persons of the existence of the study and provide interested persons with contact information for the P.I. for follow up. The Lab personnel will not inquire about health status or other personal information required of interested persons for consent. For phone inquiries the P.I. will perform an initial screening. Potential subjects will be asked if any of the following apply to them:

- Do you have any known allergy to fish?
- Are you pregnant or currently breastfeeding?
- Have you used hair dyes or treatments within the last month?
- Do you have any gastrointestinal or renal (kidney) disorders?
- Have you used antibiotics within the last month?

Subjects answering "no" to all of the above will be asked to follow up with the initial office visit.

Process of Consent

Subjects with Capacity: Only subjects with capacity will be recruited into the study. Subjects with capacity will be consented by the P.I. or study coordinator (TBD) listed on the protocol. The consent form will be reviewed with the subject directly, and the subject will also be offered the opportunity to review the consent form on their own. They will be encouraged to ask any questions and will be free to choose whether or not to participate.

Subject Comprehension: All subjects will be asked, in a private setting, if they understand all aspects of the consent form and expectations of participation in the protocol. They will be provided with contact information for the investigator and encouraged to ask for clarification at any time. Reading skills will be assessed by asking all participants, in private, if they would like any assistance in reading forms.

Documentation of Consent. All subjects will receive a signed copy of the consent form, and all consent forms will be kept on file in a locked office [name].

Costs to Subjects. There will be no costs incurred by subjects participating in the study.

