Prebiotic administration. Prebiotin™ (oligosaccharide enriched inulin), a commercially available prebiotic supplement from Jackson GI Medical (<https://www.prebiotin.com/about-us/>), will be distributed to the subjects for self-administration subsequent to the first trial and washout period and prior to the second trial (Figure 1). An intended use for Prebiotin™ is not the subject of investigation in this study. Prebiotic supplementation with this lawfully marketed over-the-counter dietary supplement is being used for its known properties of changing gut microbiome composition. Regarding FDA approval, use of Prebiotin™ in this study will be IND exempt in that all six (6) of the conditions under section 7.1 of Policy 605 of the Office of Human Subject Protection at the Univ. of Rochester are met. Briefly, with respect to Prebiotin™, this study: is not intended to support a new indication for use (7.1.1); is not intended to support a significant change in the advertising of Prebiotin™ (7.1.2); does not involve a change in route of administration, dosage level, or population at risk (7.1.3); will be conducted in compliance with the IRB review (7.1.4); will be conducted in compliance with requirements concerning the promotion and sale of Prebiotin™ (7.1.5); and, does not intend to request exception from informed consent requirements for emergency use (7.1.6). Individually packaged portions (4 grams) of the Prebiotin™ Prebiotic Fiber Stick Pac will be provided to subjects (<https://prebiotin.net/collections/our-products/products/prebiotin-prebiotic-fiber-stick-pac-4g>). Prebiotin™ is the prebiotic of choice in several published studies on gut microbiota control of obesity [20-22] and has been used in an NIH study on reducing inflammation in kidney patients [23]. For this study, we are targeting a dose of 8 grams/day. This dose amount is based on published effects of inulin on gut microbiota in the range of 4 to 16grams/day dosages [20, 24]. We have selected 8 grams/day based on the finding of Holscher et al [24], who demonstrated clear effects on shifting the microbiota composition and activity at the 7.5 gram/day dose level in healthy adults in a controlled double-blinded study. Prebiotin™ self-administration will be initiated one week prior to fish consumption in the second trial and extend through the entirety of the second trial (i.e. 11 weeks, Figure 1). Subjects will be given a 11-week supply of Prebiotin™ Stick Pacs and instructed on how to self-administer on either a once or twice daily dosing schedule. For the first week, subjects will be instructed to begin with a daily supplement of one Pac (4grams) a day, taken with meals. Starting the second week, and additional

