
Pac (2 Pacs total) will be consumed to achieve 8 grams/day. Both Pacs can be consumed at breakfast, or alternatively, divided between meals, e.g. breakfast and dinner. Prebiotin™ has a mild natural sweetness and will dissolve readily in any liquid. It can also be added to any food such as cereal, soups, salads, or sauces. If disruptive bloating or gas occurs with the 8gram dose, then the amount can be reduced to one pouch (4grams/day) until bloating and/or gas is manageable. While Prebiotin is safe to use in very high quantities, subjects will be advised on what to expect with prebiotic ingestion, including the anticipated digestive health benefits as well as possible feelings of bloating and excess flatulence that are harmless yet may produce some annoyance. Where bloating or gas is not manageable/tolerable and is disruptive to daily life, participants will be advised to contact study staff for further recommendations on reducing supplementation amounts to 2 grams/day or pursuing the option to withdraw from the study.

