8. SAFETY AND REPORTABLE EVENTS

At the first visit, subjects will be alerted to self-monitor for any adverse event and to contact study staff by phone or email with any concerns. To monitor subject adverse events, study staff will also contact subjects with a phone call or email within the week subsequent to the last fish meal in each Trial (e.g. between days 15-21 of the Trial). An additional call will be made on day "0" of Trial 2 to monitor effects of prebiotic self-administration. Study staff will not call subjects to monitor adverse events during the intermediate 4-month washout period. The most likely causes for an adverse event would be a reaction to consumption of tuna or the prebiotic administered in the second trial. Subjects will be advised to contact the P.I. by phone or email in the instance that an adverse symptom, sign, illness or experience is encountered. In the instance that this occurs before all tuna meals or prebiotic are consumed, the subject will be advised

to refrain from further fish or prebiotic consumption. Adverse events or problems are not expected but will be reported to the RSRB according to OHSP Policy 801 guidelines.

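### Screening asks about fish allergy but not about a known reaction to the prebiotic, although the protocol names both as likely causes of an adverse event

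*Combined protocol and SAP*

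**What the plan says.** Section 8 identifies two expected sources of trouble: "The most likely causes for an adverse event would be a reaction to consumption of tuna or the prebiotic administered in the second trial".

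Section 3C gives the purpose of the exclusion list: "Exclusion criteria are defined based on factors that are likely to result in either harm to the subject or" to distort the mercury metabolism or assays under study.

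The list itself, in Section 3B, has one allergy item, "Known allergy to fish". Its nearest other item is "Known gastrointestinal or renal disorders". The phone script in Section 4A mirrors these two: "Do you have any known allergy to fish" and "Do you have any gastrointestinal or renal (kidney) disorders". Callers who answer no to all five questions go on to the office visit. The information collected there (Section 5C) is age, sex, weight, dental amalgams and current medications, with no item on allergy or tolerance.

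The prebiotic is an inulin product that every subject is to take from one week before the Trial 2 fish meals to the end of Trial 2. For troublesome bloating or gas, Section 5C provides for a reduced amount and, if that fails, contact with staff about a further reduction or "pursuing the option to withdraw from the study".

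**The concern.** The protocol asks directly about one of the two exposures it expects reactions from, and not about the other. Section 1A explains that the study largely repeats two earlier protocols with the prebiotic added, and Section 3 says many of the population characteristics are carried over. The allergy item was not extended to the new product.

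The first stake is safety. A person who already knows of a reaction to inulin can enter and be scheduled for daily intake. The timing makes it worse: the prebiotic starts only after Trial 1 and a four-month washout. A person whom one phone question could have identified will by then have eaten three mercury-containing meals and given hair and stool.

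The second, lesser stake is the pre- versus post-prebiotic comparison of elimination rates in Section 11. It needs a Trial 2 value obtained under the intended exposure.

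**Working it through.** **Step 1. Does any written item reach this person?** Take a volunteer with a known allergy or earlier reaction to inulin and no known gastrointestinal or renal disorder.

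| Item | Asks about prebiotic or inulin? | Stops this person? |
|---|---|---|
| 3B allergy exclusion | No, fish only | No |
| 3B gastrointestinal or renal exclusion | No | No; it stops only those who also have a known disorder |
| 3B willingness to comply | Not directly | Only if the person declines |
| 4A phone script | No | No |
| 5C initial-visit items | No | No |
| 4A and 5C consent discussion | Not stated as a question | Only if the person volunteers it |

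No listed exclusion applies.

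**Step 2. What happens after a reaction in Trial 2?** Three routes are open on the text.

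- Reduced intake, subject retained (5C).
- Withdrawal, as an option (5C).
- Advice to refrain from further fish or prebiotic (Section 8), with no statement that participation ends or that the day-74 hair sample is cancelled. If the fish meals also stopped, the Trial 2 elimination rate would be in doubt, because 5C calibrates hair growth from the peaks of the first and last meals.

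Section 11 gives no rule for a Trial 2 value obtained on reduced or no prebiotic.

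**Step 3. The plan's own figures.**

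- Drop-out: 46 consents for 40 with data allows 6/46 = 13.0%, and 40/(1 − 6/46) = 46. This reproduces.
- Power: Section 11 claims at least 80% with 40 subjects and 19% of variance explained. By Fisher's z, with two-sided 0.05 assumed because no alpha is stated: Φ(atanh(√0.19) × √37 − 1.96) = Φ(0.467 × 6.083 − 1.96) = Φ(0.88) = 81.1%. This reproduces, but it concerns the correlation. No power is stated for the paired test.

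**Step 4. How many people?** The documents give no prevalence of known inulin allergy or reaction, so p is an assumption. Expected number = 46p. The last column is the binomial chance of seven or more among 46, treating every such person as enrolled and lost and ignoring all other drop-out.

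| Assumed p | Expected among 46 | P(at least 1) | P(7 or more) |
|---|---|---|---|
| 1% | 0.5 | 37% | below 0.001% |
| 2% | 0.9 | 61% | 0.003% |
| 5% | 2.3 | 91% | 0.8% |
| 10% | 4.6 | 99% | 17% |

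**Step 5. Cost to the paired test.** The smallest standardized difference detectable with 80% power (two-sided 0.05, noncentral t) is 0.454 with 40 pairs, 0.467 with 38, 0.480 with 36 and 0.495 with 34. Losing two pairs raises it by 0.467/0.454 − 1 = 3%; losing four, by 0.480/0.454 − 1 = 6%.

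If the same people stay in but take no prebiotic and show no effect, the mean paired difference shrinks to 38/40 = 95% or 36/40 = 90% of its full-exposure value. With the standard deviation unchanged, the full-exposure effect needed is 0.454/0.95 = 0.478 or 0.454/0.90 = 0.504. Dilution therefore costs slightly more than loss, but both are small.

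**The case against.** The best case against is that the protocol has other protections.

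- Methods, responsibilities and risks are explained before consent, and subjects must be willing to follow the procedures, of which taking the prebiotic is one. Someone who knows they cannot take it has reason to say so or decline.
- Intake starts at a lower amount in the first week, and staff call on day 0 of Trial 2 specifically about the prebiotic.
- The expected effects are described as an annoyance without further health consequence, and the documents offer no evidence on inulin allergy.

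These points stand as mitigation. They make enrolment of a known reactor less likely, but most act after exposure, and none asks the question. For fish, the protocol did not rely on disclosure; it asks. The consent form is not in the copy reviewed, so what it says about the prebiotic cannot be checked.

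A reader might infer two stronger claims. The first is that such subjects will probably be lost from the paired comparison. The text does not support this: 5C keeps them in at a reduced amount with withdrawal only an option, and Section 8 does not end participation. The second is that this gap could use up the drop-out allowance. The 17% figure needs an assumed 10% prevalence with every such person enrolled and lost; at 5% it is 0.8%. Completed Trial 1 values also remain usable in the correlation analyses.

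**Conclusion.** The gap is real and rests on the text alone: two likely causes of a reaction are named and only one is screened for, against the rationale in Section 3C. The main consequence is avoidable exposure of a foreseeable reactor, discovered only after the Trial 1 meals.

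The statistical consequence is secondary. Its size is unknown because it depends on a prevalence that the documents do not give. At assumed prevalences up to about 5%, the allowance of 46 for 40 largely covers it, and the paired test loses only a few per cent of sensitivity. The better-supported mechanism is a Trial 2 value on reduced or no prebiotic that dilutes the contrast; outright loss is one possibility. The change is worth making on grounds of safety and internal consistency, not because the analysis is endangered.

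**What to change.** Extend the allergy criterion in 3B and the first phone question in 4A to both study products, for example: *known allergy to fish, or known allergy or prior reaction to inulin or the study prebiotic that would prevent taking it in Trial 2*. Ask it before Trial 1. Keep the qualifying clause: an undefined term such as intolerance could exclude people with ordinary mild gas or bloating, whom 5C means to retain.

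The cost is one phrase in each place and a few volunteers turned away. The targets of 40 and 46 do not change.

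Two pairs of statements should be reconciled at the same time:

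- Section 5C (reduce the amount) and Section 8 (refrain) on what follows a reaction to the prebiotic. Once that is settled, Section 11 can say how Trial 2 values on reduced or no prebiotic enter the paired test.
- Section 5C (recruitment ends at 46 signed consents) and Section 7 (withdrawn subjects are replaced).
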